2.2 Secondary Objectives

2.2.1 To explore whether resistance to BRAF and MEK inhibition is associated with new functional mutations in the approximately 150 oncogenes / tumor suppressor genes that are assessed in more than 10% of the tumors (using NextGen DNA sequencing technology) in the subset of patients who co-enroll in LCCC1108, with particular focus on one of five established resistance genes (BRAF, NRAS, MEK1, MAP3K8 or COT, and PTEN)

2.2.2 To determine the overall response rate (ORR: complete response + partial response) as measured via RECISTv1.1

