KinominingTM and NextGen Sequencing (in patients who co-enroll into LCCC1108) will be done on baseline and progression biopsies to look for changes in kinome expression and mutations in resistance genes.

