4.2 Biopsies

At baseline, if patient does not have frozen tissue available (see section 6.6) fresh tissue must be obtained. If possible, the pre-treatment biopsy should be performed after all other eligibility criteria are confirmed. Enough tissue will be collected for both kinomining and NextGen sequencing if available (see section 6.6). Fresh tissue collection of accessible tumor will be repeated **at progression (clinical or radiological)** whether patient continues treatment post progression or

not. In fact, patients will be requested to remain on study medication until the biopsy at progression is performed. For subjects who are withdrawn from study treatment, but are later placed back on the trametinib/dabrafenib combination therapy, a biopsy may be collected from the former study subject at the time of progression from the standard of care trametinib/dabrafenib therapy. These subjects must be consented and placed back on study to allow for attainment of a biopsy at progression. These subjects will then remain on study for safety monitoring, in relation to the biopsy procedure, for 30 days. Subjects who have an ongoing \geq grade 2 or serious AE (SAE) related to the study procedure at 30 days will continue to be followed until the event is resolved or deemed irreversible by the investigator.

If possible, biopsies at progression should be performed within 7 business days of documented disease progression, and optimally within 4 hours of taking that day's study medication. If treating physician decides to continue treatment because the patient exhibits continued clinical benefit from therapy (and the patient agrees) then the biopsy can be delayed until the investigator deems the biopsy feasible as long as patient safety is not compromised. Post-treatment biopsies will not be required for patients removed for reasons other than disease progression; although, as mentioned above, if these subjects then go on to eventually receive the trametinib/dabrafenib combination in the future, as part of their standard of care, of the subject may be re-consented at the time of disease progression. See section 6.6 and laboratory manual. Please also see the note in section 6.9.3 regarding assessment of biopsied lesions per RECIST v1.1.

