8.0 STATISTICAL CONSIDERATIONS

8.1 Sample Size and Data Analysis Plans

Our sample size justification is based on the primary objective to identify kinases which are differentially expressed between pre (just prior to treatment initiation) and post treatment (patients who developed resistance) after treatment with BRAF+MEK inhibition in melanoma patients.

The kinases will be profiled using Multiplexed Inhibitor Beads (MIBs) coupled with mass spectrometry. We anticipate this technique to capture between 50 – 100 kinases in melanoma patients. The kinase activity is reported as a quant ratio between the experimental and control samples. The Paragon algorithm[10] automatically identifies high confidence peptides that will contribute to the average quant ratio of a kinase. Our sample size justification is based on our ability to detect a meaningful difference in the kinase activity between pre and post treatment. The inherent matching of tumor by patient source pre and post treatment will provide a potential source of positive correlation that may be exploited to improve statistical power (e.g., using a paired t-test). However, in order to be conservative, we compute our statistical power using a two-tailed independent Mann-Whitney test in which the kinase activity is compared in the two groups. Based on preliminary data, we assume that 100 kinases are captured, of which 10% of them are truly differentially expressed between pre and post treatment and a common standard deviation of 0.95 (in \log_2 scale).

Table 1 summarizes the power to detect a true difference of D with a sample size of 20 tumors in each group (pre and post treatment) at FDR of 0.05 to account for multiple testings. For example, we achieve a power of 0.92 to detect a \log_2 difference of 1.32 (or a fold change of 2.5) for each kinase between pre and post treatment.

D=Difference in \log_2 scale	1.00	1.32	1.58	1.81
Fold change (2^D)	2	2.5	3	3.5
Power	0.59	0.92	0.99	1.00

Data Analysis Plans

Exploratory tools such as heatmaps and two-way unsupervised hierarchical clustering will be utilized as visual representation of overall kinome activity. The

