univariate analysis of kinase expression will be carried out to identify differentially expressed kinases after FDR adjustment. Since multiple kinases work in concert to regulate their functions, prediction analysis of microarrays (PAM) based on nearest shrunken centroid [9] will also be carried out to identify a subset of kinases that predicts resistance to BRAF+MEK inhibition. We also plan to utilize the kinome pathway as prior information in the analysis for identifying functionally related kinase sets to improve statistical power. Focusing on kinase sets may yield more reproducible and interpretable results.

Fisher's exact test will be carried out to test for association between the mutations at baseline to mutations upon the development of resistance to BRAF + MEK inhibition in each oncogene/tumor suppressor gene. Tumor samples from patients who progress while on study and those who are removed from study and who later progress on the combination treatment will be analyzed as one data set. The p-values will be adjusted via FDR to account for multiple comparisons.

The response rate will be estimated and 95% confidence interval will be computed. Progression-free survival will be evaluated using the Kaplan-Meier method. All demographic and analytic data will be summarized by descriptive statistics. Categorical data will be summarized using frequency tables whereas summary statistics such as means, medians, standard deviation and range will be provided for continuous data.

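### The Fisher's exact test planned for mutations, as worded, measures whether baseline mutations persist; objective 2.2.1 asks about new ones, and the plan does not define an acquired mutation

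*Combined protocol and SAP*

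**What the plan says.** Objective 2.2.1 is "To explore whether resistance to BRAF and MEK inhibition is associated with new functional mutations". It covers the "approximately 150 oncogenes / tumor suppressor genes that are assessed in more than 10% of the tumors", and the sequencing is done "in the subset of patients who co-enroll in LCCC1108, with particular focus on one of five established resistance genes": BRAF, NRAS, MEK1, MAP3K8 (COT) and PTEN. Section 4.1 gives the purpose of the paired sampling: kinome profiling and sequencing "will be done on baseline and progression biopsies to look for changes in kinome expression and mutations in resistance genes".

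The only inferential analysis of mutations is in section 8.1, under Data Analysis Plans. For each gene, Fisher's "exact test will be carried out to test for association between the mutations at baseline to mutations upon the development of resistance", with FDR adjustment. Patients who progress on study and those who progress later on the combination off study are pooled. The same section plans frequency tables for categorical data in general.

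No section states the rows and columns of the table, the unit of count (patient, sample or variant), what makes a mutation new, or how pairing enters the test. Section 8.1 does recognise "The inherent matching of tumor by patient source pre and post treatment", but only for the kinase analysis.

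**The concern.** The objective is about acquisition, and the test sentence is about association between two time points. Association of baseline with later status is strongest when nothing changes, so a literal analysis would rank stable mutations first and could not flag acquired ones. An analyst who instead compares mutation frequency at the two time points would get a very different gene list from the same data. With no layout fixed in advance, that choice could be made after the data are seen.

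BRAF raises a further question. It is a named focus gene, and criterion 3.1.3 requires a V600E or V600K mutation at entry. What counts as new in BRAF therefore has to be stated.

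**Working it through.** The plan gives no sample size, power or table for this test, so there is no figure of its own to reproduce. The check compares exact p-values under the two possible layouts with a paired test.

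**Inputs.** Planned patients: 20 (section 1.1). Sequenced pairs: not stated, because only patients who co-enroll in LCCC1108 are sequenced; 20 is the upper bound, and 10 and 15 are assumed to show the range. FDR level for mutations: not stated; 0.05 is assumed, the level used for the kinases. In what follows, *kept* means mutated at both times and *gained* means mutated at progression only. No losses are assumed unless stated.

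**Layout A, literal: baseline status by progression status, one count per patient.**
- Gene wild-type in every baseline sample: the table is [[0, 0], [k, n−k]]. One margin is zero, so p = 1 for every k. This was confirmed for k = 3, 5, 8 and 10 at n = 10, 15 and 20.
- Five kept, none gained, n = 20: p = 1/C(20,5) = 1/15504 = 0.000064. At n = 15, 1/C(15,5) = 1/3003 = 0.00033. At n = 10 the table is symmetric, so the two-sided p is 2/C(10,5) = 2/252 = 0.0079.
- Five kept plus k gained, n = 20: the observed table has probability C(5+k,5)/C(20,5). For k = 3 this is 56/15504 = 0.0036, which is also the two-sided p. For k = 5 it is 252/15504, doubled by symmetry to 0.033. For k = 10 the two-sided p is 0.27. More acquisition makes the result weaker.

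**Layout B, time point by mutation status, each sample counted once.** The test is two-sided Fisher on [[kept, n−kept], [kept+gained, n−kept−gained]]. **Paired comparison:** exact McNemar, which with no losses gives p = 2 × 0.5^gained.

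| Pattern | Layout A | Layout B | Exact McNemar |
|---|---|---|---|
| 5 kept, 0 gained, n = 20 | 0.000064 | 1 | 1 |
| 0 kept, 5 gained, n = 20 | 1 | 0.047 | 0.0625 |
| 0 kept, 8 gained, n = 20 | 1 | 0.0033 | 0.0078 |
| 10 kept, 6 gained, n = 20 | 0.087 | 0.096 | 0.031 |

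Layouts A and B give opposite answers on the first and third rows.

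**Power at unadjusted 0.05, by full enumeration, with 30% of patients gaining the mutation.**

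| Pairs | 50% kept: B / McNemar | 0% kept: B / McNemar |
|---|---|---|
| 20 | 0.36 / 0.58 | 0.76 / 0.58 |
| 15 | 0.17 / 0.28 | 0.485 / 0.28 |
| 10 | 0.07 / 0.05 | 0.15 / 0.05 |

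**Type I error of layout B** at nominal 0.05, with gain and loss equally likely and non-negative within-patient correlation: at most 0.013 (n = 10), 0.017 (n = 15) and 0.022 (n = 20), over a grid of kept and gain probabilities in steps of 0.05. It is conservative under that condition.

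**BRAF coded at gene level, V600 persisting in all 20.** Layout A is [[20, 0], [0, 0]] and layout B is [[20, 0], [20, 0]]; both give p = 1 whatever secondary BRAF alteration appears.

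**FDR.** The strictest step over 150 genes is 0.05/150 = 0.00033, and over 200 genes 0.05/200 = 0.00025. Exact McNemar needs 13 gains with no losses to pass either (2 × 0.5^13 = 0.00024). With 10 pairs its smallest p is 0.002, so no single gene passes that step alone.

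**The case against.** The strongest reply is that nobody meant layout A. Objective 2.2.1 says new, section 4.1 says changes, and the kinase power statement in section 8.1 is framed as two groups, "with a sample size of 20 tumors in each group (pre and post treatment"). The Fisher sentence reads like an awkward before-and-after comparison, and an analyst holding the objective would probably build layout B. That is fair. A reader might infer that the trial set out to test persistence or cannot detect acquired mutations; the documents do not support that. Nor do they support the inference that layout B would overstate gains: with non-negative within-patient correlation it errs the other way.

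Other points that stand:
- Exact McNemar is not uniformly better. For genes wild-type at baseline it has less power than layout B (0.58 against 0.76 at 20 pairs), and at 10 pairs it gains nothing in either setting above. A claim that the plan must switch to McNemar would go too far.
- BRAF is not untestable. The p = 1 result holds only if BRAF is coded at gene level and V600 persists in every patient; the plan does not prescribe that coding.
- The general frequency tables would show how often each gene is mutated. They do not define or count acquisition within a patient.
- The LCCC1108 protocol, not available here, may define variants.
- The 10% phrase in objective 2.2.1 is ambiguous: it may limit which genes are assessed, or it may be a garbled frequency threshold for new mutations. Nothing here rests on it.

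What remains is that the written sentence describes the wrong association, and that the probable layout still leaves a new mutation undefined and the pairing unused.

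**Conclusion.** The sentence is wrong as written; severity is minor to moderate. Followed literally, it cannot detect acquired mutations in genes wild-type at baseline and gives its smallest p-values to unchanged ones. Read as probably intended, it addresses the right question conservatively, at a cost in power for genes often mutated at baseline when there are 15 or 20 pairs, and no such cost at 10. On either reading this document does not define an acquired mutation per patient and gene.

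The figures assume 10 to 20 sequenced pairs and, for the power comparison, no lost mutations; the FDR remarks assume a level of 0.05. Impact is confined to one exploratory secondary objective. The primary kinome endpoint, response and PFS are unaffected.

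**What to change.** Replace the Fisher sentence in section 8.1 with text to this effect:

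> For each sequenced patient and gene, an acquired mutation is a functional mutation present in the progression sample and absent from the paired baseline sample; for BRAF, an alteration additional to the eligibility V600 mutation. For each gene, the number acquired over the number of evaluable pairs is reported with an exact (Clopper-Pearson) 95% CI as the main output. Patients with only one sequenced sample are listed descriptively.

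If a test is kept, state whether it compares gains with losses within patient (exact McNemar) or mutation frequency by time point, that it is not a baseline-by-progression association, and the FDR level. Either test is defensible. State the number of evaluable pairs in the report, and clarify the 10% phrase in objective 2.2.1.

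**Cost.** Wording only, with no extra samples. Patients with one sequenced sample leave the paired counts. Some are likely: section 4.2 says "Post-treatment biopsies will not be required for patients removed for reasons other than disease progression", and section 6.7 gives kinome profiling priority when tissue is short. The output will be mainly descriptive, with wide intervals: 3/20 is 15% (3.2% to 37.9%), 5/20 is 25% (8.7% to 49.1%), 5/10 is 50% (18.7% to 81.3%), and 0/20 is 0% (0% to 16.8%).

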9.0 STUDY MANAGEMENT

9.1 Institutional Review Board (IRB) Approval and Consent

It is expected that the IRB will have the proper representation and function in accordance with federally mandated regulations. The IRB should approve the consent form and protocol.

In obtaining and documenting informed consent, the investigator should comply with the applicable regulatory requirement(s), and should adhere to Good Clinical Practice (GCP) and to ethical principles that have their origin in the Declaration of Helsinki.

Before recruitment and enrollment onto this study, the patient will be given a full explanation of the study and will be given the opportunity to review the consent form. Each consent form must include all the relevant elements currently required by the FDA Regulations and local or state regulations. Once this essential information has been provided to the patient and the investigator is assured that the patient understands the implications of participating in the study, the patient will be asked to give consent to participate in the study by signing an IRB-approved consent form.

Prior to a patient's participation in the trial, the written informed consent form should be signed and personally dated by the patient and by the person who conducted the informed consent discussion.

9.2 Required Documentation

Before the study can be initiated at any site, the following documentation must be provided to the Clinical Protocol Office (CPO) at the University of North Carolina.

- A copy of the official IRB approval letter for the protocol and informed consent
- IRB membership list
- CVs and medical licensure for the principal investigator and any sub-investigators who will be involved in the study.
- Form FDA 1572 appropriately filled out and signed with appropriate documentation
- CAP and CLIA Laboratory certification numbers and institution lab normal values
- Financial Disclosures
- Executed clinical research contract

9.3 Registration Procedures

All patients must be registered with the CPO at the University of North Carolina before enrollment to study. For UNC patients, prior to registration, eligibility criteria must be confirmed with the UNC Study Coordinator. To register a patient, call the Oncology Protocol Office at [contact] Monday through Friday, 9:00AM-5:00PM.

For Affiliate patients, please contact the UNCCN Study Coordinator to ensure there is an opening available on the study for the potential subject (direct line [contact]), Monday through Friday, 9:00AM-5:00PM. To register a patient, please fax registration forms and eligibility documents to [contact].

9.4 Data Management and Monitoring/Auditing

The CPO UNCCN of the UNC LCCC will serve as the coordinating center for this trial. Data will be collected through a web based clinical research platform, OnCore[®]. Other study institutions will be given a password to directly enter their own data onto the web site via electronic case report forms (eCRFs). UNCCN personnel will coordinate and manage data for quality control assurance and integrity.

All data will be collected and entered into OnCore[®] by Clinical Research Associates (CRAs) from UNC LCCC and participating institutions. The investigators at each site will allow monitors to review all source documents supporting data entered into OnCore[®]. The UNCCN Data Coordinator can be reached at [contact] or [name].

As an investigator initiated study, this trial will also be audited by the Lineberger Cancer Center compliance committee every six to twelve months depending on Affiliate site participation.

9.5 Adherence to the Protocol

Except for an emergency situation in which proper care for the protection, safety, and well-being of the study patient requires alternative treatment, the study shall be conducted exactly as described in the approved protocol.

9.5.1 Emergency Modifications

UNC and Affiliate investigators may implement a deviation from, or a change of, the protocol to eliminate an immediate hazard(s) to trial subjects without prior UNC or their respective institution's IRB/IEC approval/favorable opinion.

For Institutions Relying on UNC's IRB:

For any such emergency modification implemented, a UNC IRB modification form must be completed by UNC Research Personnel within five (5) business days of making the change.

For Institutions Relying on Their Own IRB:

For Affiliate investigators relying on their own institution's IRB, as soon as possible after the modification has been made, the implemented deviation or change and the reasons for it should be submitted to:

- To UNC Principal Investigator for agreement
- The Affiliate institution's IRB for review and approval. (Once IRB's response is received, this should be forwarded to the UNCCN Regulatory Associate).

9.5.2 Single Patient/Subject Exceptions

9.5.3 Eligibility single subject exceptions are not permitted for Lineberger Comprehensive Cancer Center Investigator Initiated Trials under any circumstances. Other types of single subject exceptions may be allowed if proper regulatory review has been completed in accordance with Lineberger Comprehensive Cancer Center's Single Subject Exceptions Policy. .Other Protocol Deviations/Violations

According to UNC's IRB, a protocol deviation is any unplanned variance from an IRB approved protocol that:

- Is generally noted or recognized after it occurs
- Has no substantive effect on the risks to research participants
- Has no substantive effect on the scientific integrity of the research plan or the value of the data collected

- Did not result from willful or knowing misconduct on the part of the investigator(s).

An unplanned protocol variance is considered a violation if the variance meets any of the following criteria:

- Has harmed or increased the risk of harm to one or more research participants.
- Has damaged the scientific integrity of the data collected for the study.
- Results from willful or knowing misconduct on the part of the investigator(s).
- Demonstrates serious or continuing noncompliance with federal regulations, State laws, or University policies.

If a deviation or violation occurs please follow the guidelines below:

For Institutions Relying on UNC's IRB:

Protocol Deviations: UNC or Affiliate personnel will record the deviation in OnCore[®], and report to any sponsor or data and safety monitoring committee in accordance with their policies. Deviations should be summarized and reported to the IRB at the time of continuing review.

Protocol Violations: Violations should be reported by UNC personnel within one (1) week of the investigator becoming aware of the event using the same IRB online mechanism used to report Unanticipated Problems.

For Institutions Relying on Their Own IRB:

In addition to adhering to the policies regarding protocol compliance set forth by your institution's IRB, the following is also required:

Protocol Deviations: In the event a deviation from protocol procedures is identified, record the deviation in OnCore[®].

Protocol Violations: Any protocol violation that occurs must be reported to your IRB per institutional policies and reported to the UNCCN Study Coordinator within 5 days. UNC-CH will determine if the violation affects the safety of the patient and integrity of the data. Once your institution's IRB response is received, please forward to the UNCCN Regulatory Associate.

Unanticipated Problems:

Affiliate Sites:

Any events that meet the criteria for "Unanticipated Problems (UPs)" as defined by UNC's IRB must also be reported to the UNCCN Study Coordinator. The UNCCN Study Coordinator will report the event to the UNC IRB using the IRB's web-based reporting system. Examples of such UPs include a lost or stolen laptop computer that contains sensitive study information.

UNC

Any events that meet the criteria for “Unanticipated Problems” as defined by UNC’s IRB must be reported by the Study Coordinator using the IRB’s web-based reporting system.

